7.1.2 Deaths, Serious and Other Significant Adverse Events

The listings of serious AEs, AE leading to study discontinuation, and subjects who died during the study will be listed.

7.2 CLINICAL LABORATORY PARAMETERS

Laboratory assessments include hematology, clinical chemistry/ phosphorus, and iron indices:

- Hematology: Hgb, Hct, RBC, WBC, MCV, MCH, MCHC, RDW, platelets, differential count and reticulocyte count.
- Clinical chemistry: sodium, potassium, chloride, BUN, creatinine, albumin, alkaline phosphatase, total bilirubin, gamma-GGT, AST, ALT, LDH, calcium, phosphorus, glucose, bicarbonate and magnesium.
- Iron indices and Phosphorus: serum iron, serum ferritin, and total iron binding capacity (TIBC), percentage serum transferrin saturation (TSAT).

- Other: urine pregnancy (if indicated), other metals (serum copper and zinc), 1,25 dihydroxy vitamin D, 25 hydroxy Vitamin D (25OH-D) and erythropoietin.

All laboratory parameters will be presented in standard units. The actual value and change from baseline will be summarized by visit and treatment group (for Phase I only) using descriptive statistics.

The number and percent of subjects with treatment-emergent potentially clinically significant (PCS) laboratory values after baseline will be summarized by visit and treatment group (for Phase I only) for each phase. The denominator is all subjects with normal baseline and at least one post baseline assessment in the safety population of that phase and the numerator is the number of subjects with PCS (i.e., meets Grade III or Grade IV toxicity criteria from the National Cancer Institute Common Terminology Criteria) at post-baseline.

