4.2.1 Inclusion Criteria

- 1. Male or female subject ≥ 18 years of age, willing and able to give informed consent.
- 2. Confirmed diagnosis of RLS based on the Cambridge-Hopkins Diagnostic Questionnaire (CHDQ) and the Hopkins-Hening Telephone Diagnostic Interview (HDTI).
- 3. IRLSS score \geq 15 plus RLS symptoms for at least 3 months and currently occurring \geq 2 nights per week.
- 4. Iron-deficiency anemia defined as an Hgb <12 g/dl with a ferritin <20 ng/mL or <100 when TSAT is <18%.
- 5. Subjects on sleep medication must be on a stable dose for at least 6 months prior screening.
- 6. Subjects at risk for pregnancy must have a negative pregnancy test at screening and be practicing an acceptable form of birth control: have had a hysterectomy or tubal ligation, or otherwise be incapable of pregnancy, or have practiced any of the following methods of contraception for at least one month prior to study entry: hormonal contraceptives, spermicide with barrier, intrauterine device, or partner sterility.

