6.4 Treatment Phase I / Treatment Phase II Assessments

6.4.1 Treatment Phase I

6.4.1.1 Day 0

The following must be obtained **PRIOR** to dosing the subject:

- Confirm the subject continues to meet the Inclusion/Exclusion criteria
 - Review medical / RLS history
 - Re-confirm IDA diagnosis
- Blood samples for hematology, iron indices, chemistries, Vitamin D, erythropoietin and trace elements
- IRLSS will be complete
- Subject will complete the following:
 - ✓ Medical Outcome Study (MOS) Sleep Scale (range 0-100)
 - ✓ Hopkins RLS-Sleep Quality Questionnaire (HRSQ)
- Vital signs to include temperature
- Concomitant medications.

Once the subject is determined to continue to meet entry criteria the unblinded treatment personnel will contact the IRT system for treatment assignment.

A separate Dosing Record will be maintained by the **unblinded treatment personnel** responsible for preparation and administration of the study drug. See Section 5.0 for details of study drug administration and precautions.

The Dosing Record will include:

- ✓ Starting and stopping time of study drug administration
- ✓ Total dose in mg and ml of FCM administered (i.e. 750 mg / 15 ml)
- ✓ Total volume of Normal Sterile Saline administered (250 ml).

The following will be obtained/conducted by **blinded study personnel** following administration of the study drug (review Sections 5.0):

- ✓ Blood pressure and heart rate, immediately post and 30 minutes post-study drug administration
- \checkmark Adverse events, starting with the first dose of study drug
- ✓ If there are no significant signs or symptoms at the 30 minute post-study drug vital sign assessments, the subject will be released.

6.4.1.2 Day 7

The following must be obtained in the following order:

- Adverse Events
- Vital signs to include temperature
- Concomitant medications
- Blood samples for hematology, iron indices, chemistries, and Vitamin D
- Study drug dosing.

A separate Dosing Record will be maintained by the **unblinded treatment personnel** responsible for preparation and administration of the study drug. See Section 5.0 for details of study drug administration and precautions.

The Dosing Record will include:

- ✓ Starting and stopping time of study drug administration
- ✓ Total dose in mg and ml of FCM administered (i.e. 750 mg / 15 ml)
- ✓ Total volume of Normal Sterile Saline administered (250 ml).

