7. SAFETY ANALYSIS

All safety analyses will be performed on the Safety Population. No formal statistical testing will be performed for safety. Safety assessments include:

- Adverse events
- Laboratory assessments (hematology, iron indices, chemistry, and other)
- Vital signs

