7.3 VITAL SIGNS AND PHYSICAL EXAMINATION FINDINGS

7.3.1 Vital Signs

Vital signs will be collected for Phase I and Phase II, include sitting body temperature, blood pressure (BP) and heart rate. On study drug dosing days BP and heart rate will be collected immediately pre-dosing, immediately and 30 minutes post dosing, and body temperature will be collected on the dosing dates.

All vital signs will be presented in conventional units as in Table 3. Frequency and percentage of subjects with values considered PCS occurring at post-baseline in dosing days will be summarized by visit and by treatment group (for Phase I only) for each Phase. The denominator is all subjects with a baseline assessment in the full analysis population and the numerator is the number of subjects with PCS at post-baseline. Criteria for PCS are presented below Table 2.

Table 2 Criteria for Potentially Clinically Significant Vital Signs

Vital Sign	Criterion	Definition of PCS at Any Post-baseline Time Point
Systolic blood pressure	Low	Value ≤ 90 mmHg and decreased ≥ 20 mmHg [1]
	High	Value ≥ 180 mmHg and increased ≥ 20 mmHg [1]
Diastolic blood pressure	Low	Value ≤ 50 mmHg and decreased ≥ 15 mmHg [1]
	High	Value ≥ 105 mmHg and increased ≥ 15 mmHg [1]
Pulse	Low	Value ≤ 50 bpm and decreased ≥ 15 bpm [1]
	High	Value ≥ 120 bpm and increased ≥ 15 bpm [1]

[1] For immediately and 30 minutes post-dose assessments on Dosing Days, the change (decrease or increase) is based on the pre-dose value obtained on each corresponding dosing day.

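### The laboratory PCS percentage in SAP 7.2 rests on an undefined normal baseline and does not clearly count numerator and denominator in the same subjects; SAP 7.3.1 uses a population the SAP does not define.

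*SAP*

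**What the plan says.** SAP 7.2 plans a summary of "The number and percent of subjects with treatment-emergent potentially clinically significant (PCS) laboratory values after baseline", by visit for each phase and by arm in Phase I. Two clauses build the percentage. The first is "The denominator is all subjects with normal baseline and at least one post baseline assessment", taken within each phase's Safety population. The second is "the numerator is the number of subjects with PCS (i.e., meets Grade III or Grade IV toxicity criteria", assessed after baseline. The SAP does not say what normal means and gives no reference ranges. Treatment-emergent is defined in SAP 7.1 for adverse events only.

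Protocol 4.2.1 requires, for both sexes, "Iron-deficiency anemia defined as an Hgb <12 g/dl with a ferritin <20 ng/mL or <100 when TSAT is <18" per cent. Protocol 6.4.1 lists "Re-confirm IDA diagnosis" among the Day 0 checks before dosing.

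SAP 2.1 sets the baselines:
- Phase I: the last value before randomized drug.
- Phase II: the last value before the unblinded FCM of that phase.
- Phase III: Day 0 of Phase I for Phase I responders, and Day 0 of Phase II for Phase II responders.

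For vital signs, SAP 7.3.1 says "The denominator is all subjects with a baseline assessment in the full analysis population". SAP section 7 opens with "All safety analyses will be performed on the Safety Population". SAP 2.2 defines an ITT and a Safety population and no other.

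**The concern.** A percentage of subjects needs a numerator drawn from its denominator. SAP 7.2 does not secure this, and its one explicit baseline condition suits this trial poorly because anaemia is an entry requirement. For red-cell parameters the rule could remove most or all subjects. For parameters that Phase I treatment may have moved, it removes subjects according to what happened to them in Phase I.

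This is the only planned summary of Grade III/IV laboratory toxicity taken directly from measured values. A wrong or empty percentage there would not be corrected by another table of the same kind. The vital-sign table has a separate fault: its denominator names a population that the SAP does not define.

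**Working it through.** The documents state no PCS rate, so there is no figure to reproduce. The check compares set definitions and adds illustrative counts under labelled assumptions.

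**1. The ratio in general.** For one parameter and phase, let N be the Safety-population subjects with a post-baseline value and A those among them with an abnormal baseline. Let x_n and x_a be the numbers reaching Grade III/IV from a normal and an abnormal baseline.

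- Unrestricted numerator: (x_n + x_a) / (N − A). Once A > 0 and there is any event, this exceeds (x_n + x_a) / N. It passes 100% if x_n + x_a > N − A and is undefined if A = N.
- Restricted numerator: x_n / (N − A). All of x_a disappears.

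The two faults belong to different readings and cannot both occur.

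**2. Haemoglobin, Phase I.** Inputs: baseline below 12 g/dL for all (Protocol 4.2.1, re-confirmed on Day 0) and planned N = 70 (Protocol 8.1). The LLN is not given, so it is varied. Two baseline distributions are assumed: uniform on 8 to 12 g/dL, with expected count 70 × (12 − LLN)/4; and normal with mean 10.5 and SD 1.2 truncated at 12, with expected count 70 × [F(12) − F(LLN)]/F(12), F being the normal distribution function.

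| Assumed LLN (g/dL) | Uniform | Truncated normal |
|---|---|---|
| 12.0 or higher | 0 | 0 |
| 11.7 | 5.3 | 4.1 |
| 11.5 | 8.8 | 7.6 |
| 11.0 | 17.5 | 18.2 |

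So the denominator is empty at an LLN of 12 or higher, and about 4 to 18 of 70 at 11.7 to 11.0. Phase III uses the same Day 0 baseline for Phase I responders. The Phase II baseline follows Phase I treatment, so haemoglobin can be normal by then.

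**3. Phosphorus, Phase II.** The Phase II laboratory criteria in Protocol 6.4.2 are ferritin and TSAT only, so a subject below the phosphorus LLN can enter and then falls outside the denominator. To size this, assume the planning CGI-I rates (50% and 15%) stand in for response, all non-responders enter, and low baseline phosphorus occurs only in prior-FCM subjects.

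- Prior FCM: 35 × 0.50 = 17.5. Prior placebo: 35 × 0.85 = 29.75. Total: 47.25.
- If 10%, 30% or 50% of prior-FCM subjects start low, 1.75, 5.25 or 8.75 subjects leave the denominator (3.7%, 11.1% or 18.5% of 47.25).

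Take the 30% case, with assumed Grade III/IV rates of 5% from a normal baseline and 30% from a low one. The normal-baseline group is 47.25 − 5.25 = 42. Events are 42 × 0.05 = 2.1 and 5.25 × 0.30 = 1.575.

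- Unrestricted: 3.675 / 42 = 8.75%.
- Restricted: 2.1 / 42 = 5.0%.
- All subjects: 3.675 / 47.25 = 7.8%.

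With a low-baseline rate of 10% or 60% instead, the unrestricted figure is 6.25% or 12.5%, the all-subject figure 5.6% or 11.1%, and the restricted figure stays at 5.0%. One reading overstates and the other understates.

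**4. Vital signs.** The only full analysis set in either document is in Protocol 8.2. For Phase I it needs post-randomization IRLSS and CGI-I measurements. The schedule of events places CGI-I at Day 42 only, while Protocol 4.4 asks for final procedures at withdrawal. Under that reading, a subject who left early with no CGI-I would be missing from a table of dosing-day vital signs.

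**The case against.** The lead sentence of SAP 7.2 says treatment-emergent, and a number-and-percent table is ordinarily counted within its denominator. A programmer may well restrict the numerator. Normal could also be meant as not PCS at baseline, which would remove most of the problem. Both points are fair, but neither reading is written down, so the wording does not settle which table will be produced.

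A reader might infer that the haemoglobin rate is undefined throughout the trial. The documents do not support that. It needs normal to mean within the reference range and an LLN of at least 12 g/dL, which is not stated, and it need not apply in Phase II.

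A reader might also infer that subjects with low phosphorus vanish from the safety report. They do not. Hypophosphatemia is an adverse event of special interest with no baseline restriction (SAP 7.1.1), actual values and changes are summarised by visit (SAP 7.2), and phosphate is listed by subject and visit (SAP 6.3.1). These outputs lessen the harm. They do not supply a Grade III/IV rate from measured values, since Protocol 7.1 makes a laboratory value an adverse event only when it is judged a clinically significant worsening. That low-phosphorus subjects are the most likely to progress is a reasonable inference, but the documents do not say so.

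The loss of early leavers from the vital-sign table is only possible. SAP section 7 points to the Safety population, the protocol's FAS accepts any post-randomization CGI-I, and final procedures are due at withdrawal. The FAS also comes from the supplied protocol, approved in April 2016, whereas the SAP cites a protocol dated 4 September 2019.

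Finally, the study ended early and safety has no formal testing (SAP sections 7 and 9), so no decision rule depends on these percentages.

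**Conclusion.** Wrong as written, with impact limited to descriptive safety tables. The laboratory PCS rule leaves normal undefined and does not clearly put numerator and denominator on the same subjects. Its result is either inflated or omits everyone who worsens from an abnormal baseline.

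For Phase I haemoglobin, and for Phase III in Phase I responders, few or no subjects are evaluable: none if the LLN is 12 g/dL or higher, and in Phase I about 4 to 18 of 70 at 11.7 to 11.0. This assumes that normal means within the reference range, that the stated baseline distributions hold, and that the Day 0 value used as baseline still meets the entry limit. Seventy is the planned number, not the analysed one.

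The size of the Phase II phosphorus effect cannot be derived from the documents; the figures above show direction only. The population named in SAP 7.3.1 is a definite internal conflict, while its effect on early leavers is a possibility.

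**What to change.** In SAP 7.2, make the denominator all Safety-population subjects of the phase who are not already Grade III/IV for that parameter at the phase baseline and who have at least one post-baseline value. State that the numerator is counted only among those subjects. This removes the need to define normal and gives treatment-emergent a meaning for laboratory data: a move into Grade III/IV.

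In SAP 7.3.1, replace the full analysis population with the Safety population of that phase having a pre-dose and at least one post-dose value.

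Optionally, add a table of baseline grade against worst post-baseline grade for all treated subjects by phase, with Phase II phosphorus split by Phase I arm.

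The cost is revised wording in two SAP sections and a changed programming filter, plus the shift table if wanted. No new data are needed.

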7.3 VITAL SIGNS AND PHYSICAL EXAMINATION FINDINGS

7.3.1 Vital Signs

Vital signs will be collected for Phase I and Phase II, include sitting body temperature, blood pressure (BP) and heart rate. On study drug dosing days BP and heart rate will be collected immediately pre-dosing, immediately and 30 minutes post dosing, and body temperature will be collected on the dosing dates.

All vital signs will be presented in conventional units as in Table 3. Frequency and percentage of subjects with values considered PCS occurring at post-baseline in dosing days will be summarized by visit and by treatment group (for Phase I only) for each Phase. The denominator is all subjects with a baseline assessment in the full analysis population and the numerator is the number of subjects with PCS at post-baseline. Criteria for PCS are presented below Table 2.

Table 2 Criteria for Potentially Clinically Significant Vital Signs

Vital Sign	Criterion	Definition of PCS at Any Post-baseline Time Point
Systolic blood pressure	Low	Value ≤ 90 mmHg and decreased ≥ 20 mmHg [1]
	High	Value ≥ 180 mmHg and increased ≥ 20 mmHg [1]
Diastolic blood pressure	Low	Value ≤ 50 mmHg and decreased ≥ 15 mmHg [1]
	High	Value ≥ 105 mmHg and increased ≥ 15 mmHg [1]
Pulse	Low	Value ≤ 50 bpm and decreased ≥ 15 bpm [1]
	High	Value ≥ 120 bpm and increased ≥ 15 bpm [1]

[1] For immediately and 30 minutes post-dose assessments on Dosing Days, the change (decrease or increase) is based on the pre-dose value obtained on each corresponding dosing day.

7.3.2 Physical Examination

Any significant findings from physical examinations will be documented in medical history or adverse events.

7.4 OTHER ANALYSES

Cambridge-Hopkins Diagnostic Questionnaire (CHDQ), Hopkins-Henning Telephone Diagnostic Interview (HTDI), Hopkins RLS-Sleep Quality Questionnaire (HRSQ), and urine

8. INTERIM ANALYSES AND DATA AND SAFETY MONITORING BOARD (DSMB)

8.1 INTERIM ANALYSES

No formal interim analysis is planned for this study.

8.2 DATA AND SAFETY MONITORING BOARD (DSMB)

No Data Safety Monitoring Board for this study.

9. SUMMARY OF MAJOR CHANGES IN THE PLANNED ANALYSES

Compared with the study protocol 1VIT15042 (Date: 4 September 2019), below items are the major changes made in this SAP:

1. Due to early termination of the study, no statistical analysis will be performed. Hence no primary, and secondary end points will not be tested with statistical model.
2. Physical examinations was removed from safety analysis list and any significant findings will go to medical history or adverse event summaries.
3. The secondary endpoint “Number of Subjects who remained in the study to Week 52” will be summarized in disposition table for n (%) of study completer. It will not be considered as an efficacy endpoint in this SAP.
4. Adverse events of special interest were added in this SAP in Section 7.1.1.
